Magnesium (Mg) is an important intracellular ion with electrophysiological properties. It is essential for optimal metabolic cell function. Mg has proven effective for treating eclampsia, preeclampsia, and torsade's de pointes. Other therapeutic applications such as adjunctive therapy in acute asthma exacerbations, acute coronary syndromes, acute cerebral ischemia, and postoperative pain control are under discussion. (5)

Some studies have shown that serum hypomagnesaemia is common after coronary artery bypass grafts (CABG) and other types of cardiac surgery. (6) and is associated with postoperative morbidity such as atrial tachyarrhythmia.(7)

Some clinical trials have assessed the efficacy of magnesium as a method of intervention to reduce the incidence of postoperative AF.(8)

2. AIM/ OBJECTIVES (Maximum 300 words)

The primary aim of this study is to investigate the anti-arrhythmic effect of Magnesium Sulfate in prevention of atrial fibrillation post cardiac surgery.

3. METHODOLOGY:

Patients and Methods/ Subjects and Methods/ Material and Methods (Maximum 1000 words) *“References may be needed”*

This study is a prospective, randomized controlled trial that will study the postoperative anti-arrhythmic effect of Magnesium Sulfate and clinical outcomes of administration of intravenous Mg Sulfate in patients undergoing open heart surgery.

Randomization will be performed using a computer-generated randomization sequence and allocation concealment to be maintained all through the time of procedure, by using opaque, numbered, and sealed envelopes.

The study protocol will receive ethical approval from the Research Ethical Committee/ Institutional Review Boards, Faculty of Medicine Ain Shams University.

Informed consent will be obtained from each patient before patients' allocation.

Type of the study: prospective randomized clinical trial study protocol.

Study Setting: The operating theaters and ICU of Cardiothoracic institute of Ain Shams University Hospitals.

Study period: one year.

Sample Size:

Using PASS 15 program for sample size calculation, setting power at 80% and alpha error at 0.05, it is estimated that sample size of 65 patients per group (Total 130 patients) can detect an expected medium effect size ($h= 0.50$) for the difference between two groups regarding incidence of post-operative AF using a two-sided z test.

Study population:

Inclusion criteria:

- Age group: Adult patients from age of 18 years to 70 years
- Sex: Both sexes

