Total time of Mg/placebo infusion is 24 hours, and oral tablets for 1 week just before hospital discharge.

Total serum Magnesium level will be measured immediately post weaning of cardiopulmonary bypass, on ICU arrival, after 24 and 48 hours.

Both groups will receive standardized antiarrhythmic medications as per institutional protocols.

Endpoints of the study:

Primary end point:

1. Evaluation of incidence of atrial fibrillation during hospital stay.

Secondary end points:

1. Total ICU stay.
2. Incidence of new postoperative renal impairment
3. Total ventilation time
4. Incidence of readmission with AF during same hospital stay

Ethical considerations:

The study protocol will receive ethical approval from the Research Ethical Committee, Faculty of Medicine Ain Shams University.

Informed consent will be obtained from each patient before patients' allocation.

Statistical Analysis

Based on published meta-analyses reporting AF incidence of 30–40% in controls following cardiac surgery (Cook et al., 2013(11); Klinger et al., 2015(12)) and anticipating a 50% relative risk reduction (RRR) with our optimized Mg protocol (higher bolus dose, post-CPB initiation), we estimated a medium effect size ($h=0.50$). This RRR assumption was derived from:

- Pharmacokinetic data confirming serum Mg levels >2.5 mg/dL reduce AF risk by 45–60% (Fairley et al., 2015(6); Shiga et al., 2004(13))
- Prior positive RCTs using similar high-bolus regimens (2–3g) showing 54–60% RRR (Miller et al., 2005 (14); Kaplan et al., 2003(15))

Using PASS 15, with power=80% and $\alpha=0.05$, a sample size of 65 patients per group (total N=130) provides 85% power to detect an absolute risk reduction of 20% (control:40% , Mg:20%). This aligns with RCTs detecting similar effects in cardiac surgery cohorts (Gu et al., 2012; N=60–100/group (9)). Continuous variables were analyzed using independent t-tests or ANCOVA (adjusted for covariates); non-parametric data employed Mann-Whitney U tests. Categorical outcomes used chi-square or Fisher's exact tests. Multivariable logistic regression adjusted for age, body mass index (BMI), chronic obstructive pulmonary disease (COPD), diabetes status,

ejection fraction (EF), surgery type, and left atrial size (where available). Sensitivity analyses included propensity score matching (PSM) and Bayesian posterior probability estimation.

4. REFERENCES (Maximum 20 references)

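### With about 39 AF events for nine slopes, the planned logistic model overstates the adjusted log odds ratio by about 10–12%, and the plan has no rule for missing left atrial size; a standardised risk difference and baseline imputation deal with both.

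*Combined protocol and SAP*

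**What the plan says.** The Sample Size section plans for a "sample size of 65 patients per group (Total 130 patients", "setting power at 80% and alpha error at 0.05", "using a two-sided z test". The Statistical Analysis section restates the target: to "detect an absolute risk reduction of 20% (control:40% , Mg:20"%. It quotes control AF rates of 30–40% from earlier meta-analyses and assumes that magnesium halves the risk.

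For binary outcomes the same section names chi-square or Fisher tests. It then adds "Multivariable logistic regression adjusted for age, body mass index (BMI), chronic obstructive pulmonary disease (COPD), diabetes status". The covariate list goes on to include "ejection fraction (EF), surgery type, and left atrial size (where available"). The inclusion criteria admit three kinds of operation: CABG, valve replacement, and both combined.

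The plan does not name the outcome of the logistic model, although AF is the natural reading. It does not say whether this model or the unadjusted test is primary. It specifies no penalisation, no marginal effect measure, and no rule for patients whose left atrial size is missing.

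**The concern.** Maximum-likelihood logistic regression is biased in small samples: when events are few for the number of coefficients, estimates move away from zero. Here the covariate list is long for the expected number of events, so the adjusted odds ratio would on average make magnesium look better than it is, even if the model were exactly right.

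The words on availability of left atrial size add a second problem. They concede that the variable may be missing for some patients. Standard software then drops those patients without warning, which removes randomised patients and their events from the adjusted analysis. What is at stake is the size of the reported adjusted effect and the power of that analysis.

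**Working it through.** **1. The plan's own figures.** For h = 0.50, two-sided alpha 0.05 and 80% power: n = 2 × ((1.96 + 0.8416)/0.50)² = 62.8, so 63 per group. The stated 65 is consistent with this. The statement that "a sample size of 65 patients per group (total N=130) provides 85% power" at 40% vs 20% does not reproduce. With the pooled z test, (0.20 × √65 − 1.96 × √(2 × 0.3 × 0.7)) / √(0.24 + 0.16) = (1.612 − 1.270)/0.632 = 0.541, which is 70.6% power. That is a separate matter; below I use only 65 per group and the two rates.

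**2. Events.** 0.40 × 65 + 0.20 × 65 = 26 + 13 = 39. At the lower end of the plan's control range with the same halving, 0.30 × 65 + 0.15 × 65 = 19.5 + 9.75 = 29.25.

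**3. Slopes.** Treatment 1, age 1, BMI 1, COPD 1, diabetes 1, EF 1, surgery type 2 (three categories), left atrial size 1: nine in all. This assumes linear continuous terms and binary COPD and diabetes. Events per slope: 39/9 = 4.3, or 29.25/9 = 3.25.

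**4. Bias of the adjusted odds ratio.** Trials of 130 patients, 1:1, were simulated with marginal AF of 40% vs 20%. Covariate distributions and strengths are assumptions, because the documents give none. The mean nine-slope estimate was compared with the true conditional log odds ratio, so the differences below are small-sample bias and not non-collapsibility. There were 8,000 trials per row; Monte Carlo SE of the bias is 0.5 points.

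| Covariates | Bias of log OR | SD of estimate | Power, nine-slope Wald | Power, risk difference from nine-slope model |
|---|---|---|---|---|
| Not prognostic | +10.4% | 0.46 | 70.2% | 71.5% |
| Moderate | +10.9% | 0.50 | 74.1% | 75.5% |
| Moderate, spread over all | +11.6% | 0.53 | 74.8% | 76.5% |

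For moderate covariates the true value is −1.08 (OR 0.34) and the mean estimate −1.20 (OR 0.30): 1.20/1.08 = 1.11. At 30% vs 15% the bias reached about 14%. The excess of 0.12 against an SD of 0.50 is about a quarter of a standard error. Coverage of the nominal 95% Wald interval was 94.1–94.3%.

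**5. Standardised risk difference.** Fit the nine-slope model, predict each patient's risk under magnesium and under placebo, and average the difference: RD = (1/N) Σ [p̂(1, xᵢ) − p̂(0, xᵢ)]. Its mean was −0.198 to −0.202 against a true −0.20. Its false-positive rate was about 5.6–6.4%, against 5.1–6.0% for the planned Wald test.

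**6. Firth penalisation of the nine-slope model.** Mean estimate −1.08 against a true −1.08. Power of the penalised test was 71.5%, against 73.6% for Wald, and its false-positive rate was 4.8%.

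**7. A shorter model.** With treatment, age, surgery type and left atrial size (five slopes) there are 39/5 = 7.8 events per slope. The log odds ratio is still about 6–7% too large. Power of its risk difference was 71.6%, 75.0% and 73.8% in the three rows above. In the last row that is 76.5 − 73.8 = 2.7 points below the full model's risk difference.

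**8. Missing left atrial size.** At an assumed 20% missing, complete cases leave 0.8 × 130 = 104 patients and 0.8 × 39 = 31.2 events, or 3.5 per slope. Simulated power fell to 62–64%, from about 71–74% with complete data, and the bias rose to about 15%. With imputation, power was about 72–75%. At an assumed 30% missing, complete-case power was 58% and bias about 18%. Power figures from different runs differ by about a point; with 2,500 trials the Monte Carlo SE is √(0.72 × 0.28/2500) = 0.9 points.

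**The case against.** The strongest reply is that the adjusted odds ratio may not carry the trial's conclusion. The trial is sized on a z test of two proportions, and chi-square or Fisher is named before the logistic model. That points to the unadjusted comparison, which this bias does not touch. A reader might infer that the trial's main result will be overstated; the documents do not support that, because they never call the logistic model primary. They do not call the unadjusted test primary either, so the adjusted odds ratio could still end up as the reported result.

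Second, the effect on inference is small: about a fifth to a quarter of a standard error, with near-nominal coverage. This stands. The point concerns the estimate and does not invalidate the test.

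Third, a reader might infer that the covariate list has to be cut and that cutting it is free. Neither follows. Changing the effect measure removes the bias with all nine slopes in place, whereas the five-slope odds ratio remains biased. Nothing in the documents ranks left atrial size or surgery type above BMI, COPD, diabetes or EF, and dropping prognostic covariates costs power.

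Fourth, the note on availability could mean that left atrial size is omitted from the model if it is not collected, and not that patients are dropped. The plan does not say. The loss of power is therefore conditional on complete-case analysis and on the assumed share missing.

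**Conclusion.** The concern holds in limited form. If the logistic model is fitted to AF by ordinary maximum likelihood as listed, its treatment log odds ratio will be about 10–12% too large at 40% vs 20%, and up to about 14% too large at 30% vs 15%. The bias is present even when the covariates are not prognostic, so it does not depend on the assumed covariate strengths; its exact size varies a little with them. The result rests on nine slopes, on the plan's own rates and on no dropout, since none is stated.

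Complete-case handling of left atrial size could matter more in practice, at roughly 10 points of power for an assumed 20% missing. The true share missing is unknown.

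This is a worthwhile, inexpensive correction to how the adjusted effect is estimated and reported.

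**What to change.** In the Statistical Analysis section:

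- State whether the unadjusted or the adjusted comparison of AF incidence is primary, and name the outcome of the logistic model.
- Keep the listed covariates. Report the adjusted effect as a risk difference standardised over all randomised patients (g-computation), with a 95% CI. This also matches the absolute scale on which the target effect is stated.
- Fill missing left atrial size by a simple baseline imputation, blind to outcome and arm, so that every randomised patient stays in the model.
- If an adjusted odds ratio is also reported, estimate it with Firth penalisation and profile-likelihood intervals.

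The cost is wording and slightly more analysis work; no added patients or data are needed. The risk-difference test can run slightly liberal, so specify a small-sample standard error. Using Firth for testing costs about 2 points of power (73.6 − 71.5 = 2.1). A shorter covariate list is optional; it is not needed to remove the bias, and it can cost power if the dropped covariates are prognostic.

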- Elective open heart surgeries for coronary bypass grafting CABG, valvular lesion single or multiple replacement, combined CABG and valvular; with EF in preoperative echo is more than or equal 40%

Exclusion criteria:

- Patients refuse to give informed consent.
- Emergency open heart surgeries
- Redo cases.
- Patients with preoperative serum creatinine level ≥ 1.8 mg/dL

- Patients with reduced intra/post operative urine output ≤ 1 ml/kg/hour.
- Patients with Chronic Kidney disease, Renal failure on dialysis
- Patients with rhythm defects as proved by ECG before administration of Mg/Placebo.

Sampling method:

Patients will be randomly allocated by computer generated randomization into two groups A and B:

- **Group A (Study group):** patients receiving Intravenous Mg Sulfate.
- **Group B (Control):** patients receiving Placebo drug.

Anesthetic management:

Full standard preoperative assessment for cardiac surgery will be done for all patients included in the study before planned procedures.

Premedication will be given according to standard protocol in cardiac anesthesia. Routine monitoring included a five-lead electrocardiogram, pulse oximeter and invasive blood pressure. Anesthesia will be induced with midazolam 0.02mg/kg and fentanyl 2-5 microgram /kg and muscle relaxation were achieved cisatracurium 0.15 mg/kg intravenous. After tracheal intubation, central venous line and TEE inserted, then anesthesia will be maintained throughout the procedure with morphin20 microgram/kg /min, cisatracurium 2mg/kg/min and sevoflurane 2%. Ventilation will be adjusted to maintain end-tidal carbon dioxide in the range of 30-40 mmHg.

Then after completion of surgical procedure and successful weaning off Cardiopulmonary bypass the patients will be divided into two groups group A will receive 2 gm of Mg Sulfate diluted in 30 cc normal 0.9 % saline via intravenous infusion over 1 hour (1 Mg sulfate ampoule = 10 cc) and group B will receive 50 cc normal 0.9 % saline via intravenous infusion over same period.

On ICU arrival group A will continue receiving 1 gm of Mg sulfate per hour for five hours via continuous IV infusion, while group B will receive same volume and rate of normal saline.

After 5 hours, group A will receive 200 mg of Mg sulfate per hour for 19 hours via continuous IV infusion, then oral replacement of mag added 1 gm/8 hours tablet, while group B will receive same fluid volume and rate of normal saline followed by oral inert starch tablets.

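### Propensity score matching is a poor sensitivity analysis for this randomised trial, and the urine-output exclusion can remove patients from the AF comparison after allocation

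*Combined protocol and SAP*

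**What the plan says.** The primary end point is AF incidence during the hospital stay. For the analysis, the Statistical Analysis section lists:

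- An unadjusted test: "Categorical outcomes used chi-square or" Fisher's exact, with no rule for choosing between them.
- A multivariable logistic regression whose covariates end with "surgery type, and left atrial size (where available").
- Then: "Sensitivity analyses included propensity score matching (PSM) and Bayesian posterior probability estimation". No matching ratio, caliper or covariate set is given.

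No analysis population is defined and none of these analyses is labelled primary. The Sample Size paragraph does size the trial "regarding incidence of post-operative AF using a two-sided z test".

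On design, the Methodology section describes a computer-generated sequence in sealed envelopes, with "allocation concealment to be maintained all through the time of procedure". Under Anesthetic management, the two groups are formed after weaning from bypass, and the infusion then starts. The Exclusion criteria nevertheless include "Patients with reduced intra/post operative urine output" at or below a stated threshold.

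On left atrial size, the Inclusion criteria call for patients "with EF in preoperative echo is more than or equal 40" per cent, and "Full standard preoperative assessment for cardiac surgery will be done for all patients". An echo should therefore exist for every patient, although the text asks it for ejection fraction, not left atrial size.

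**The concern.** Propensity score matching is meant for comparisons in which treatment was chosen for reasons related to prognosis. With concealed 1:1 randomisation, every patient's true probability of receiving magnesium is one half. Estimated scores then differ between arms only by chance. A caliper discards patients whose chance score has no close partner in the other arm. The result is a smaller, noisier comparison that can differ visibly from the all-patient one. A reader who sees the two disagree may take it as evidence that the main result is fragile, when most of the movement is sampling noise.

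The urine-output criterion raises a different problem. Urine output after the infusion starts is measured after allocation. The plan itself lists new postoperative renal impairment as a secondary outcome, so it treats renal function as something that may differ by arm. Excluding patients on such a variable can undo the balance that randomisation gives, and it would affect every AF analysis, including the unadjusted test.

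**Working it through.** **Design figures.** The plan gives no figure for matching. Its own figures for the AF comparison are 65 per group, h = 0.50, 80% power, and 85% power for 40% versus 20%.

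- From h: n = 2 × ((1.960 + 0.842)/0.50)² = 62.8, so 63 per group. The stated 65 is consistent with this.
- At 40% versus 20% (pooled variance, two-sided 0.05): (0.20 × √65 − 1.960 × √0.42)/√0.40 = (1.612 − 1.270)/0.632 = 0.541, which gives 70.6% power. The stated 85% does not reproduce. That is a separate matter, but it leaves little room for losing patients.

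**Matching: simulation.** There were 65 patients per arm, AF risk 40% versus 20%, and 4,000–8,000 replicates (Monte Carlo SE at most 0.8 points). Matching was greedy 1:1 nearest neighbour without replacement on the logit score, compared unpaired. The following inputs are assumptions, not in the documents:

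- Age, BMI and EF: standard normal, odds ratios per SD 1.5, 1.1 and 0.85.
- COPD: 10% prevalence, OR 1.5. Diabetes: 35%, OR 1.2.
- CABG/valve/combined: 50/35/15%, OR 1/1.5/2.0.
- Left atrial size: OR 1.4 per unit.

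| Assumed caliper (SD) | Pairs kept of 65 | Patients discarded | SD of risk difference (points) | SD of departure from all-patient result (points) | Departure over 5 points |
|---|---|---|---|---|---|
| 0.1 | 43.8 | 33% | 9.4 | 5.9 | 39% |
| 0.2 | 48.5 | 25% | 8.8 | 5.1 | 32% |
| 0.5 | 52.4 | 19% | 8.5 | 4.4 | 24% |
| none | 65 | 0% | 7.8 | 0 | 0% |

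Over repeated runs the SD of the matched estimate ranged from 8.3 to 9.4 points, and departures over 5 points from 24% to 41%. The average departure was at most 0.2 points, so no systematic bias is being removed. With no caliper, an unpaired 1:1 comparison of equal arms is the full comparison again.

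**Checks by formula.**

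- Discarded share: 1 − 43.8/65 = 33%; 1 − 48.5/65 = 25%; 1 − 52.4/65 = 19%.
- Unadjusted SD: √((0.40 × 0.60 + 0.20 × 0.80)/65) = √(0.40/65) = 7.8 points.
- The same formula at 43.8, 48.5 and 52.4 per arm gives 9.6, 9.1 and 8.7 points. The simulated 9.4, 8.8 and 8.5 are slightly smaller because matching corrects some chance imbalance.
- Treating departures as normal with SD 5.9, 5.1 and 4.4, the chance of exceeding 5 points is about 40%, 33% and 26%, close to the simulated values.

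**The alternative on all 130.** The standardised risk difference from the logistic model has SD 7.9 points and departs by more than 5 points in 9% of trials.

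**Choice of test.** With no true effect (30% in both arms), chi-square alone gives p < 0.05 in 5.0% of trials. Taking whichever of chi-square and the adjusted model is significant gives 7.2% (7.0–7.5% in repeat runs).

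**Urine output.** The documents give no rate for this criterion, so any bias cannot be sized. If losses were equal by arm, an assumed 10% would lower the 70.6% power to 65.9%, and 20% to 60.7%.

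**The case against.** Much can be said for the plan. Matching is labelled a sensitivity analysis, so it is not offered as a route to the main claim. No caliper is stated, so the loss of patients is assumed, not documented. The covariate effects are also assumed. Matching is not pure noise either. At a 0.2 SD caliper it cut the SD of chance prognostic imbalance from 2.2 to 1.2 points, and its departure from the all-patient result correlates about 0.55 with that of the adjusted estimate. The urine-output criterion may have been meant as screening before allocation.

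These points rule out several stronger readings that a reader might infer:

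- *A disagreement after matching carries no information.* Too strong, given the correlation of 0.55. The supported statement is that matching is an inefficient adjustment.
- *The false-positive rate is 8.2–8.8%.* That counts the matched analysis as a route to a claim, and the plan already ranks it lower. About 7% is the supportable figure.
- *The plan has no primary AF test.* The Sample Size paragraph ties AF to a two-sided z test, which equals the uncorrected chi-square. What is missing is mainly the label.
- *The logistic model will drop patients without left atrial size.* The wording could equally mean leaving the covariate out. The plan does not say.

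What remains is that matching has no confounding to remove, loses precision if a caliper is used and adds nothing in the unpaired 1:1 form without one. The urine-output exclusion, read as written, extends past allocation.

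**Conclusion.** The concern holds in two parts. First, propensity score matching should be replaced. With a caliper of 0.1–0.5 SD it would discard about 19–33% of patients, widen the SD of the risk difference from about 7.8 to 8.3–9.4 points, and move the estimate by more than 5 points in about 24–41% of trials, against a target difference of 20 points. These sizes depend on the assumed calipers and covariate effects. The absence of systematic confounding depends only on randomisation and on keeping everyone who was randomised. Second, the urine-output exclusion can break that condition, to an extent the documents do not allow one to size.

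The unadjusted chi-square result is not affected by the matching or left atrial points, but it is exposed to the urine-output exclusion. The missing primary label and missing-data rule are smaller gaps, worth closing in the same edit. The Bayesian estimate is not at issue here.

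**What to change.** 1. Replace matching with a supportive covariate-adjusted (standardised) risk difference and robust 95% CI, from the planned logistic model fitted to all randomised patients. Take left atrial size from the preoperative echo and fill any gap with the overall mean, computed without regard to arm, so that nobody is dropped.
2. State that the AF comparison includes all randomised patients as allocated, including any who meet the urine-output criterion after allocation. This concerns the analysis set only, not clinical handling.
3. Label the uncorrected chi-square test, with the risk difference and 95% CI, as the primary AF analysis. It matches the test used for sizing. The smallest expected count is 65 × 0.30 = 19.5, so Fisher's test is not needed.

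The cost is SAP wording, one data field and a little code, with no extra patients. The main downside is a thin adjusted model: 65 × (0.40 + 0.20) = 39 expected events for 9 terms, or 4.3 per term. In simulation its log odds ratio is overstated by about 11–13%, which is why the risk difference should be reported. It fails to converge in 0.5–0.8% of trials (about 2.5% at 30% versus 15%), so a linear regression on the same covariates should be named as fallback. The ordinary large-sample interval covers only 92.7–93.4%. An HC3-type interval with that fallback covers 95.4–96.2%, but excludes zero less often than chi-square is significant (69.1% versus 72.0%). The adjusted result should therefore stay supportive only.
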